Pilot Project Programme for Prevention of Falls among Community-dwelling Elderly in Guangzhou

Guangzhou Centre for Disease Control and Prevention

June 2024

Table of Content

I. BACKGROUND OF THE STUDY	3
II. OBJECTIVES OF THE STUDY	6
III. STUDY SUBJECTS	7
IV. INTERVENTION STRATEGIES	10
V. MAIN INTERVENTION ACTIVITIES	11
VI. PROJECT EVALUATION	15
VII. METHODS OF STATISTICAL ANALYSIS	27
VIII. SAFETY GUARANTEE	29
IX. QUALITY CONTROL	30
X. RESEARCH FLOW CHART	35
XI. ORGANISATIONAL MANAGEMENT AND DIVISION OF RESPONSIBILITIES	36

Pilot Project Programme on Prevention of Falls among Community-dwelling Elderly in Guangzhou

I. Background of the study

According to China's seventh population census, the population aged 60 and above reached 264 million in 2020, accounting for 18.7 per cent of the total population, and by 2025, the total number of elderly people will exceed 300 million. Falls are the leading cause of injury and death among the elderly, and 20-30 per cent of elderly people who recover from fall-related injuries will suffer a decline in self-care ability or even premature death. Currently, China has a large elderly population in urban communities, and falls among the elderly have become a public health issue of public concern. In 2019, the State Council issued the Opinions on the Implementation of Healthy China Actions, which emphasises "accelerating the promotion of the shift from treating illnesses as the centre of health care to people's health as the centre of health care", and will "Implementing health promotion actions for the elderly" as an important part of maintaining health throughout the life cycle. Falls in the elderly are not an accident, but the result of the interaction of multiple risk factors. Most of these risk factors can be changed and prevented. At this stage, the majority of older people in our city live in the community, and about 61.7 per cent of falls occur at home or in other community settings. The community is the main venue for the implementation of the strategy of "prevention first, moving the gate forward, and lowering the centre of gravity" for the prevention and control of chronic diseases. However, there are no evidence-based scientific and systematic intervention techniques, models and tools that can be directly scaled up in our city. In 2022, there will be only 16.84 public health doctors and 112 public health nurses per 100,000 people in our city, and public health services are severely under-resourced

due to the surge in the number of patients suffering from chronic diseases such as diabetes and high blood pressure. The healthcare system is also facing an increasing economic burden and unprecedented challenges. Therefore, it is important to explore a fall prevention intervention service model that meets the city's economic, cultural, and environmental conditions under limited community healthcare resources, so that more older adults can benefit from fall prevention intervention services to improve the quality of life of older adults and to reduce the burden of healthcare.

Risk factors for falls in older people include gait and balance disorders, visual impairment, syncope and arrhythmia, irrational use of medication, foot disorders and environmental hazards. Intervention studies on falls in the elderly began in developed regions and countries in the 1980s, and the studies were mainly divided into two categories: single-factor interventions targeting a single risk factor and multifactorial interventions targeting multiple risk factors. Since the 1990s, there has been a gradual increase in the number of multifactorial intervention studies on falls in older adults in developed countries, and the number of high-quality randomised controlled studies has also gradually increased. Existing evidence suggests that targeted interventions targeting the various risk factors for falls in older adults are the most effective strategy for preventing falls in older adults. Population-based community-based integrated interventions that address single risk factors, such as improving balance function and home environment, can also be effective in preventing falls in older adults and reducing the severity of injuries caused by falls. Based on this, the research group organised two rounds of the project "Research on the Effectiveness of Community-Based Intervention of Health Education Group Activities for Fall Prevention in the Elderly" in 2020 and 2022 in some communities in Guangzhou. The project is a multifactorial intervention based on the community population, through the implementation of seven health education programmes, including fall risk assessment and management, health self-management skills, exercise guidance, rational use of medication, and one

door-to-door modification of the fall-related hazardous environment. Twelve months after the first round of the project, the incidence of falls in the intervention group was 4.35%, compared with 24% in the control group, $p < 0.05$. Both rounds of the project were effective in raising the awareness of fall prevention and the level of fall prevention knowledge and skills among the elderly, and reducing the number of falls, which resulted in a better intervention effect.

However, the intervention programme of seven health education classes and one home assessment in the pre-programme, if it needs to be widely promoted in our city, may put more pressure on the existing working mode of primary healthcare institutions, and the curriculum needs to be streamlined for easy promotion. In addition, the effectiveness of individual intervention components was not studied in the pre-intervention, and the mechanism of action of individual elements of the intervention with respect to outcome effects could not be confirmed. When the performance of individual intervention components is unknown, it is not clear which factor has the least effect on outcomes. The components selected for removal may be the main cause of any effects observed in the RCT, and therefore may result in a streamlined intervention that is less effective or even ineffective.

Therefore, this study intends to build on the results of the previous research, selecting community elderly in Baiyun District as the intervention target, assessing the fall risk factors of the intervention target through qualitative analysis of fall risk, and targeting the formation of health education activity groups; the intervention target of each group randomly receives different combinations of interventions under the guidance of professional and technical personnel; and evaluating the effects of different interventions through a randomised controlled trial with analytic factor design to screen the The effectiveness of different interventions will be evaluated through a randomised controlled trial with a causal analysis design, in order to screen the comprehensive intervention elements, optimise the mode of intervention combinations, and save the research

resources and costs; furthermore, the study will provide scientific references and practical tools for the city to carry out the fall intervention services for the elderly applicable to the primary healthcare institutions, and ultimately reduce the incidence of falls among the elderly, and improve the quality of their lives.

II. Objectives of the Study

(1) General objectives of the study

Using a multi-stage optimisation strategy, the group will optimise the project intervention programme in the improvement phase, conduct a randomised controlled trial using a factorial design, quantitatively compare the effects of different falls programmes on falls prevention, carry out an economic evaluation of the different intervention groups, and ultimately determine the optimal combination of intervention strategies for the project. To explore and establish a community-based falls prevention intervention model for the elderly, and to provide a scientific basis and a practical tool for the establishment of a community-based falls prevention service model for the elderly that is suitable for implementation by primary healthcare organisations in the city. Ultimately, through city-wide dissemination and implementation, we will achieve the goal of reducing the incidence of falls among older adults and improving their quality of life.

(2) Specific objectives

1. To be achieved through a 2-month intervention for the target population within 12 months after the start of the implementation of the intervention:

1.1 Apply a multi-stage optimisation strategy, centred on an analytic design randomised controlled trial, to screen for elements of a community falls prevention intervention for older people and optimise a comprehensive intervention management strategy for community falls prevention in older people;

1.2 Evaluate the inputs and outputs of the multifactorial intervention strategy for the prevention of falls in older people, to provide a basis for the dissemination of the intervention strategy and government decision-making.

III. Study subjects

The researcher used the Screening Form for Research Subjects (Annex 2) to select eligible elderly people as research subjects among the elderly population by means of questionnaires and scale assessments.

(1) Study subjects

All 24 streets within Baiyun District of Guangzhou City were included in the study area. Sampling should take into account the state of socio-economic development, the age of the population, the gender ratio of the neighbourhood committees (villages) as consistent as possible, and the balanced distribution of the sample; taking into account the principle of cost-effectiveness and the feasibility of the sampling scheme. Through centralised open recruitment, household recruitment and other forms of recruitment, followed by face-to-face survey, telephone survey, on-site assessment, etc., eligible elderly people are selected as intervention research subjects and randomly assigned to each intervention group.

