1.1.3 Requirements for the proportion of recruited subjects

In order to increase the homogeneity of study subjects, study subjects can be recruited with reference to the following gender and age requirements:

① 20% male, 80% female; ② 30%-35% aged 60-65 years, ③ 30%-35% aged 66-70 years, ④ 30%-35% aged 71-75 years, ⑤ less than 10% aged 76-80 years.

(2) Sample size estimation

After scientific calculations, combined with the actual work, a total of 888 people are needed for this project, then each group needs a sample size of $n=111$, and a total of 37 people are recruited in each street (town). The sample size calculation process is as follows:

This study uses the dichotomous variable "whether a fall occurs" as the outcome indicator. According to the results of the occurrence of falls among the elderly in the community in Guangzhou City in 2023, the incidence of falls among the elderly in Baiyun District was 17%. After discussion with experts, it was concluded that a 35% reduction in the incidence of falls after the intervention was considered to be of public health significance. In this study, the test level was set at $\alpha=0.05$ and the test efficacy at 0.8 (i.e., $\beta=0.2$). The proposed factorial design for this study is based on the sample size formula (below) for factorial designs in which the outcome variable is a dichotomous variable, and the sample size required for each test condition can be obtained as:

$$n = \frac{(Z_{1-\alpha/2} + Z_{1-\beta})^2}{2^k [\arcsin(\sqrt{\frac{\rho+\rho\delta}{2}}) - \arcsin(\sqrt{\frac{\rho-\rho\delta}{2}})]^2} \approx 83$$

$$\rho=0.17, \delta=0.35, Z_{1-\alpha/2}=1.96, Z_{1-\beta}=0.84, k=3.$$

The total sample size required for the 8 test conditions was:

$$N_{\text{conditions}} = 83 \times 8 = 664$$

According to S. Bhasin, T.M et al, the design effect of whole cluster randomisation can be obtained by estimating $ICC = 0.0076$ and mean number of individuals in the cluster $m = 28$:

$$DE = 1 + (m-1) \times ICC = 1 + (28-1) \times 0.0076 = 1.2052$$

The sample size was set to be the same for the eight test conditions, and the total sample size required for the study was:

$$N = N_{\text{conditions}} \times DE \div (1 - 10\%) \approx 888$$

The required sample size for each test condition was then 111 cases;

Each of the 24 streets recruited 37 study participants.

(3) Intervention groups

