The study subjects were grouped in a completely randomised manner, with a statistician independent of the research team using a computer to generate random numbers, and equal proportions of the study subjects recruited from the 24 streets (towns) were allocated to the 8 experimental condition groups, so that each experimental condition contained all the study subjects from 3 streets (towns). After grouping was completed, a database of basic information about the study participants was created, as shown in Table 1. This study was blinded only to the data collectors and data analysers.

Table 1 Subgroups of the Community Falls Prevention for Older People Pilot Project

groups	Fall Prevention Education Course	Development of personal exercise skills	Environmental assessment
Group 1	Yes	Yes	Yes
Group 2	Yes	Yes	No
Group 3	Yes	No	Yes
Group 4	Yes	No	No
Group 5	No	No	No
Group 6	No	Yes	Yes
Group 7	No	Yes	No
Group 8	No	No	Yes

IV. Intervention Strategies

(1) Strategy 1: Falls prevention education programme

To organise the research subjects in the intervention group to set up a fall prevention health education activity group, in which the project team will disseminate knowledge and concepts of fall prevention through lectures, discussions, questions and answers, and sharing, so as to enhance the knowledge base required by the research subjects to prevent falls and to cultivate the relevant concepts.

(2) Strategy 2: Developing personal exercise skills

Through lectures, demonstrations, on-site exercises and practices, the project team taught the intervention group participants to improve their balance function, lower limb muscle strength, endurance exercise and other fall prevention exercise skills, and to use fall prevention aids through group activities.

(3) Strategy 3: Environmental Assessment

Through the staff's home assessment and guidance, the project team instructed the study participants to assess the risk factors of fall-related home environment and made suggestions for modification.

V. Main intervention activities

(1) Strategy 1: Fall prevention education programme:

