SPSS20.0 was used for statistical processing. Variables such as general demographic characteristics, disease characteristics, previous falls, and level of social support at baseline were compared to see if there were any differences between the different intervention groups, and variables with differences would be corrected in the subsequent analyses. Intent-to-treat (ITT) analysis is proposed to evaluate the intervention in this study. Descriptive analysis: statistical descriptions of primary outcome variables, secondary outcome variables, intervention implementation and other synergistic factors, etc., and independent samples t-tests (continuous variables such as Older Adult Falls Efficacy Scale scores, Quality of Life Scale scores, Older Adults' Falls Knowledge and Belief Behaviour Scale scores, etc.) and chi-square tests (categorical variables such as attitudes towards the intervention strategy, incidence of falls, etc.) to compare the between-groups differences were used.

The study proposes to assess the economic benefits using Incremental Cost-Effectiveness Ratio (ICER), which is the increased cost per unit of effect.

VIII. Safety Guarantee

- (1) When carrying out the various screening, assessment, training, exercise and other activities of the project, the safety and physical health of the research subjects should be ensured as the first principle.
- (2) During the various screening and assessment processes, research subjects should be clearly informed of the testing methods and possible risks. The project may conduct demonstrations and allow research subjects to practise before taking formal measurements. The staff should remind the participants that they should not pursue "good results" in the test.
- (3) In the process of training and exercise, the basic principles are gradual and according to one's ability, and research subjects should not be forced to perform movements that are beyond their ability. All exercises are subject to the subjective feeling of the research subjects themselves, while attention should be paid to correcting the research subjects' sense of "not obeying the old" and stopping dangerous actions in time.

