7.2 Hidden group information in the database

Groups are coded in the database using group codes that are not recognisable to analysts, ensuring that data analysts do not know which intervention group the study participant is in by using the group information in the database.

X. Research flow chart

[figure not shown]

Figure 1 Project Flowchart
 Note: Work completed in yellow

XI. Organisational management and division of responsibilities

(1) Guangzhou Centre for Disease Control and Prevention

Overall responsible for the project work, formulate the work plan, organise expert demonstration, pre-test, organise the implementation of intervention, evaluation and summary. It is responsible for conducting first-level training, overall implementation of quality control work, and work supervision. According to the project programme, select the project site area and clarify the division of responsibilities among the cooperation units. Responsible for coordinating the cooperation units in the district, carrying out training, implementing interventions, implementing quality control work requirements, guiding the implementation of evaluation and other work, and organising work supervision.

(2) CDC of the project site area

According to the project programme, it is responsible for implementing and coordinating the project communities/sections to carry out intervention activities, implementing training, assessment, quality control, and daily management of the project.

(3) Community Health Service Centre of the project site

Organise and implement the project work in the district and implement the quality control requirements.

广州市疾病预防控制中心医学研究伦理审批件

研究名称	社区老年人预防跌倒方案构建研究：基于多阶段优化策略的随机对照试验
研究分类	预防医学
负责人	[name]
审批编号	GZCDC-ECHR-2024P0116

(项目简介 1、研究时间；2、研究内容；3、研究人群范围；4、采用方法 5、知情同意及保障措施)

项目研究时间：从 2024 年 6 月至 2027 年 6 月

研究内容：基于前期研究成果，健康教育课程+发展个人运动技能+环境评估干预方案，并通过检验不同干预组别跌倒效果，评估不同组别的投入-产出，筛选出最经济最优化的干预方案，解决原干预方案耗时长，较难全面推广的问题，为我市开展适用于基层医疗卫生机构实施的老年人跌倒干预服务提供科学参考和实用工具。

研究人群范围：招募 888 名年龄为 60~80 岁（含 60 岁和 80 岁）的社区常住老年人。

采用方法：在改善阶段对前期项目有效的干预方案进行改良，利用部分析因设计进行随机对照试验，定量定性比较不同跌倒方案对于预防跌倒的效果，开展不同干预方案的经济学评估。

知情同意及保障措施：项目开展前每个研究对象均需签署知情同意书，为保证整个项目安全进行，每次集中授课均需考虑天气等因素，并派

医务人员给予医疗保障。

经广州市疾病预防控制中心伦理委员会讨论，认为该研究所涉及的内容符合《涉及人的生物医学研究伦理审查办法》（中华人民共和国国家卫生和计划生育委员会令第11号）的要求，同意开展研究。

广州市疾病预防控制中心伦理委员会

2024年6月3日

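### The plan picks the optimal combination from this trial's own data with no selection rule and no correction for selection, so an effect or ICER for the chosen package taken from those data would be biased towards benefit.

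*Combined protocol and SAP*

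**What the plan says.** Section II (1) sets out a factorial randomised trial in the improvement phase of a multi-stage optimisation strategy, with an economic evaluation of the groups. The trial is to "ultimately determine the optimal combination of intervention strategies for the project". The same paragraph ends: "Ultimately, through city-wide dissemination and implementation, we will achieve the goal of reducing the incidence of falls among older adults". Objective 1.2 adds that the results are meant to inform dissemination and government decisions.

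The ethics approval at the end of the document describes the aim as "筛选出最经济最优化的干预方案", that is, to screen out the most economical and optimal programme. Cost is therefore a criterion alongside falls.

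Section III (3) says that participants "were allocated to the 8 experimental condition groups", with three streets in each. Table 1 is a full 2×2×2 layout: seven groups receive at least one component, and Group 5 receives none.

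For falls, section VII (2) gives intention-to-treat, correction for baseline variables that differ, and chi-square tests "to compare the between-groups differences were used". It then names an ICER. It states no factorial model, selection rule, multiplicity control or shrinkage. It does not say how the chosen combination's effect will be estimated, or against which comparator.

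**The concern.** When several noisy estimates are compared and the most favourable is kept, the kept estimate is too favourable on average, even if each estimate is unbiased alone. This holds for choosing the lowest of several group fall rates. It also holds, less strongly, for keeping the components whose main effects point the right way.

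The recommended package is the trial's main product. Its effect would be the denominator of the ICER and would support any case for wider use. The sample-size section treats a 35% relative reduction as worthwhile for public health. At a 17% base rate that is 0.35 × 17 = 5.95 percentage points (pp). If selection alone can produce an apparent benefit near that size, an uncorrected figure cannot show that the target was met.

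**Working it through.** **Inputs.** From section III (2): base rate 17%, target reduction 35%, ICC 0.0076, 37 recruited per street, 10% loss, "Z_{1-\alpha/2}=1.96, Z_{1-\beta}=0.84, k=3". From section III (3): eight conditions with three streets each. Analysed per street: 37 × 0.9 = 33.3, taken as 33, so 99 per condition. My assumptions are whole streets per condition, 17% everywhere under no effect, and the selection rules below, because the plan states none.

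**The plan's own figure.** Its arcsine formula gives 83.5 per condition (stated 83). Then 83 × 8 = 664 and 664 × 1.2052 / 0.9 = 889.2 (stated 888 = 24 × 37). The planned size reproduces.

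**Standard errors.**
- Design effect at 33 per street: 1 + 32 × 0.0076 = 1.2432.
- One group's fall rate: √(0.17 × 0.83 / 99 × 1.2432) = 4.21 pp.
- One main effect (four groups against four): 4.21 / √2 = 2.98 pp.

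**Rule A: lowest of the seven active groups, on falls alone.** The expected minimum of seven normal values lies 1.3522 SE below the mean: 1.3522 × 4.21 = 5.7 pp. Simulation of 200,000 trials with beta-binomial streets, which respects the discreteness and skew of the rates, gives:
- 5.5 pp below observed Group 5, which is 5.5 / 17 = 32% of the base rate;
- a per-trial relative reduction (1 − best / Group 5) with mean 27% and median 31–32%;
- an apparent reduction of 35% or more in about 44–45% of trials.

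**Rule B: keep every component with a favourable main effect.** Each component adds on average 2.98 × 0.399 = 1.19 pp of spurious benefit. Three give 3.6 pp, or 21% of 17%. Simulations give 3.4 to 3.6 pp.

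**Rule C: keep a component only if it is favourable at two-sided p<0.05.** The plan's test level is borrowed here as a selection threshold.
- With a clustered SE: 3 × 2.98 × φ(1.96) = 3 × 2.98 × 0.0584 = 0.5 pp. Some component is kept in 1 − 0.975³ = 7% of trials.
- If clustering is ignored: about 0.8 pp, with some component kept in 11% of trials.
- In the trials where something is kept, the spurious effect is still about 7 pp (0.52 / 0.073 = 7.1).

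**When one component truly works (35% reduction).** Under rule A the chosen group shows about 9.5 pp against a true 5.6 to 5.7 pp, an excess of nearly 4 pp.

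**Sensitivity of rule A.** With 111 analysed per condition and no clustering, the apparent reduction reaches 35% in 34% of trials and the mean per-trial reduction is 24%. The base rate matters too. Measured against the true rate, the lowest of seven is 22–26% below it at 24% fallers and 35–40% below it at 11.05%.

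**Does a correction work?** A parametric bootstrap simulates from the fitted factorial model, repeats the selection and subtracts the mean optimism. Applied to the model-based estimate, it gives:

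| Scenario | Uncorrected | Corrected | Truth |
|---|---|---|---|
| No effect | 3.5 pp | 1.0 pp | 0 |
| One component works | 8.1 pp | 6.3 pp | 5.8–5.9 pp |

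Root mean squared error falls in both scenarios. It rises slightly, from 3.9 to 4.1 pp, when all three components work modestly.

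**The case against.** Three points on the other side have force.

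1. **The plan never says it will report the raw best group against Group 5.** A reader might infer this, since the between-group chi-square test is the only falls comparison written down, but it remains an inference. What stands is that the plan needs an effect for the ICER, names no estimator for it, and describes no source other than this trial.

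2. **A flat 32% is not supported.** It requires choosing the lowest group on falls alone, and it divides a mean difference by 17%. The documents point partly elsewhere: the sample-size formula pools conditions as for main effects, the text speaks of screening elements, and cost is a criterion. Rules of that kind give about 20%, or 3–5% (0.5 / 17 to 0.8 / 17) on average with a p<0.05 threshold. The bias does not vanish: under the strict rule it is concentrated in the few trials where a component is kept.

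3. **Roll-out straight after this trial is not stated.** The dissemination sentence expresses an eventual goal. The ethics approval runs to June 2027 although fall collection ends in May 2025, and the flow chart is not available here. A later evaluation is possible, but the text describes none.

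It can also be said that no correction for selection can be run until a rule exists to repeat. That is right, and it makes the rule the first part of the remedy.

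**Conclusion.** The concern holds in conditional form. The trial selects its recommended combination from its own data, and the plan has no selection rule, no correction and no described confirmation. An effect or ICER for the chosen package drawn from the same data would be biased towards benefit.

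With no true effect, the average bias is about 5.5 pp under lowest-group selection, about 3.5 pp under favourable-sign selection of components, and 0.5 to 0.8 pp under a p<0.05 rule. These figures rest on a 17% base rate in every condition, three streets per condition, 33 analysed per street and ICC 0.0076. No simulation included cost as a criterion, because the plan does not say how it enters.

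This does not invalidate the trial or its randomised comparisons. It concerns the headline estimate for the recommended package and what is built on it.

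**What to change.** In section VII (2), before group codes are opened:

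1. State the selection rule, including how cost enters.
2. Estimate the chosen package's effect from the factorial model with a street effect, not from the raw best group against Group 5.
3. Report that estimate with a selection-corrected value, for example from a parametric bootstrap that repeats the stated rule in each replicate.
4. Use the corrected value in the ICER and in any dissemination claim.
5. Label the raw best-group contrast with Group 5 as descriptive.
6. Check by simulation that the corrected interval has acceptable coverage with only 24 streets.

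**Cost.** Analysis work only, with no added participants, visits or data. It is more than a small addition to the listed t-tests and chi-square tests, because a clustered factorial model must be specified first. The headline effect will look less favourable. About 1 pp of bias remains under no effect, and error rises slightly in some scenarios.
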